To include the options of recall coordinated from within participating practices and centralised recall coordinated by the Primary Health Organisation (PHO).

To screen at least 3000 patients using their choice of one of the following tests:

- Vaginal hrHPV self-test performed at home or other suitable location
- Vaginal hrHPV self-test performed at the General Practice (GP) clinic (with or without nurse or kaiāwhina-led support)
- Clinician-taken cervical liquid-based cytology sample.

To implement NCSP-agreed care pathways for abnormal hrHPV screening results utilising cervical cytology, colposcopy and repeat screening.

To implement NCSP-agreed screening and care pathways for patients with previous abnormal cytology.

Objectives

Primary

To describe the impact of hrHPV testing (by demographics and screening history when numbers permit) in terms of:

- Proportion of patients screened by each method
- Proportion of patients who complete or do not complete each step of the appropriate screening pathway (including uptake of screening, cytology triage, and colposcopy assessment) and referral back to primary care
- Time to completion of the appropriate screening pathway
- Screening outcomes in patients with prior abnormalities in relation to transition guideline recommendations
- Number of colposcopy referrals, their indication, and outcomes.

To describe the disease burden detected in the study population, in terms of:

- HPV positivity rate by HPV 16/18 or other hrHPV, by demographics
- Incidence of CIN2+ in patients with HPV 16/18 by cytology result
- Incidence of CIN2+ in patients and with other hrHPV with abnormal cytology.

Secondary

To describe uptake of screening by mode of invitation:

- Centralised PHO or practice-based recall.

To describe resource utilisation (e.g. number of contacts, type of contact, engagement of other agencies, cost to patient) to achieve completion of the screening pathway:

- To achieve hrHPV screen
- In the event of an abnormal hrHPV screen, to achieve cervical cytology and/or colposcopy.

To report the rate of unsatisfactory hrHPV samples or documentation.

Equity

Compared to the general population, Māori and Pacific patients are less well served by the NCSP based in traditional primary care practices. The reason for introducing the HPV self-test is to reduce the incidence of cervical cancer and reduce inequities by providing a more sensitive test and reducing barriers to cervical screening.

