Data from participating patients will be collected within participating practices and from the central study site on a secure web-based REDCap database stored on a secure University of Otago server.

Data sources include practice screening registry, NCSPR, consent, practice records, and laboratory results (cytology, histology, hrHPV, colposcopy records). Data will be anonymised prior to analysis.

Specimen storage /disposal

Specimen storage /disposal will be as per NCSP/ laboratory protocol (please see Tissue Management Plan for detail).

Outcome measures

HrHPV TESTING
The number (and percentage) of participants with: 1,2,3 or >3 attempts to be contacted prior to their hrHPV test.
The mean, median and range for time from the first study appointment to an hrHPV test being conducted, for each participant.
The mean, median and range for time from the first contact attempt to an hrHPV test being conducted, for each participant.
The number (and percentage) of participants who were successfully contacted to take part in the study by: 
 - Letter - Text - Opportunistic invitation at their GP clinic - A face to face appointment with a staff member at their GP clinic - A phone call with a staff member from their GP clinic - Other form of contact.
The mean, median and range for the time from the first study appointment to an hrHPV test being conducted, for each participant.
The mean, median and range for the time from an hrHPV test being undertaken to being received by the laboratory for analysis, for each participant.
The number (and percentage) of participants that undertook a: 
 - Vaginal test at home - Vaginal test at their GP clinic without staff assistance - Vaginal test at their GP clinic with staff assistance - Cervical test without concurrent cytology - Cervical test with concurrent cytology.
The mean, median and range of charges (NZD) for each type of hrHPV test listed under the outcome above. This will be reported by whether the tests were subsidised or not.
The mean, median and range for the time from an hrHPV test to the results report being issued.

UNSATISFACTORY hrHPV TESTS
In participants who underwent hrHPV testing and had an unsatisfactory result, the reason for that result: 
 - Incorrect labelling - Sample unsatisfactory

HPV-based Screening Implementation Study Protocol

- Other

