- LSIL (low grade squamous intraepithelial lesion)
- ASC-H (atypical cells of undetermined significance, possible high grade)
- HSIL (high grade squamous intraepithelial lesion)
- Cancer (invasive squamous carcinoma of the cervix)
- Adenocarcinoma
- Cancer other
- AGC/AIS (atypical glandular cells / adenocarcinoma-in-situ)
- Unsatisfactory sample

Data to be presented separately for participants negative for hrHPV, participants positive for HPV16 and/or 18, and participants positive for hrHPV other than 16 or 18.

In participants that had colposcopy, the number (and percentage) that had a visualised result of:

- Unsatisfactory,
- No abnormality detected
- CIN1
- CIN2
- CIN3
- Adenocarcinoma
- Squamous cell carcinoma
- Other

Data to be presented separately for participants negative for hrHPV, participants positive for HPV16 and/or 18, and participants positive for hrHPV other than 16 or 18.

In participants that had colposcopy, the number (and percentage) that had the transformation zone visualised.

Data to be presented separately for participants negative for hrHPV, participants positive for HPV16 and/or 18, and participants positive for hrHPV other than 16 or 18.

In participants that had colposcopy, the number (and percentage) that had a biopsy.

Data to be presented separately for participants negative for hrHPV, participants positive for HPV16 and/or 18, and participants positive for hrHPV other than 16 or 18.

In participants that had colposcopy with a biopsy, the number (and percentage) that had a visualised result of:

- Unsatisfactory
- No abnormality detected
- CIN1
- CIN2
- CIN3
- Adenocarcinoma
- Squamous cell carcinoma
- Other

Data to be presented separately for participants negative for hrHPV, participants positive for HPV16 and/or 18, and participants positive for hrHPV other than 16 or 18.

In participants that had colposcopy, the number (and percentage) that had each treatment recommendation.

Data to be presented separately for participants negative for hrHPV, participants positive for HPV16 and/or 18, and participants positive for hrHPV other than 16 or 18.

In participants that had colposcopy, the number (and percentage) that had each treatment.

Data to be presented separately for participants negative for hrHPV, participants positive for HPV16 and/or 18, and participants positive for hrHPV other than 16 or 18.

HPV-based Screening Implementation Study Protocol

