The mean, median and range for times from colposcopy to initiation of each of the treatments in the outcome above.

Data to be presented separately for participants negative for hrHPV, participants positive for HPV16 and/or 18, and participants positive for hrHPV other than 16 or 18.

Incidence of CIN2+ in participants by cytology result.

Data to be presented separately for participants negative for hrHPV, participants positive for HPV16 and/or 18, and participants positive for hrHPV other than 16 or 18.

OTHER

Where numbers permit, all outcomes will be presented by:

- Screening history (previously undergone cervical treatment/had an abnormal cervical screen, or not)
- Age band (<25, 25-34 years, 35 to 54 years, 55-69, >69 years), self-reported ethnicity (NZ European/other, Māori, Pacific Island or Asian)
- Socioeconomic deprivation index (Quintiles 1 through to 5)
- Region (Christchurch, Wellington or Whanganui and surrounding areas)

Mean, median and range for the per participant cost (NZD) to the participant's GP clinic for each of the following:

- hrHPV self-test at home or clinic without support
- hrHPV self-test at clinic with support
- hrHPV cervical test by a nurse
- hrHPV cervical test by a doctor
- Cytology test as part of hrHPV cervical test
- Cytology test performed separately to the hrHPV test
- Colposcopy referral.

The number of patients at participating clinics who are due or overdue for cervical cancer screening during the six-month screening period that did not take part in the study (deidentified data). Of these patients, the number (and percentage) that: did have cervical cytology during the screening period and did not have cervical cytology during the screening period.

Statistical Considerations

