Serious adverse events will be reported to the study management team by filling out a Serious Adverse Event (SAE) report form and emailed within 7 days of the GP practice becoming aware of the event.

Serious Adverse Events include:

- Interval diagnosis of invasive cancer, CIN3, or AIS following a negative hrHPV test
- A screened person being given the wrong result
- A screened person being given the wrong advice following their screen (e.g., not referred to colposcopy or cytology when they should have been)
- A screened person not receiving the result of a positive test

Serious adverse events will be investigated as soon as possible by the study team and the relevant service provider to ensure similar errors do not occur and that there is no systemic case for this error.

The service provider will be responsible for the discussion of this adverse event with the person affected and their whanau and informing other agencies if appropriate. The study team will be responsible for informing the NCSP.

The following other adverse events will also be reported at completion of the study

- A person referred to colposcopy who does not attend within 3 months
- A person with other hrHPV who is recommended to have cervical cytology but who does not attend within 3 months

Site visits

Site visits will be performed either face to face or virtually by at least 1 member of the study management team, prior to commencing invitation to the study and within 3 months of commencing the study. Additional visits will be organised on request of the participating practice or if issues are perceived by the study management team.

The first visit is to ensure mechanisms of enrolment data management and clinical management of patients is understood by all members of the team. In addition, to ensure that systems are appropriate.

The second visit is to understand any issues of concern being encountered by the practice and to ensure ongoing participation of the practice team with screening and study protocols.

Further site visits may occur as required if areas of concern have been identified.

Audit

Prospectively-collected data will be collected in electronic case report forms (e-CRF) within 4 weeks of the event. 10% of data will be audited against source documents. If more than 10% of data is missing or incorrect, further in-depth audit will be undertaken.

Quality assurance

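### The biopsy outcome is worded as a visual result, so no listed outcome reports histology, and the CIN2+ outcome lacks a reference standard and denominator and extends beyond its objective

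*Protocol*

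**What the plan says.** Two adjacent items under Outcome measures, COLPOSCOPY, report results. The first reads "In participants that had colposcopy, the number (and percentage) that had a visualised result of" and lists eight categories: unsatisfactory, no abnormality, CIN1, CIN2, CIN3, adenocarcinoma, squamous cell carcinoma and other. The second reads "In participants that had colposcopy with a biopsy, the number (and percentage) that had a visualised result of" and lists the same eight.

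The last item of that table is "Incidence of CIN2+ in participants by cytology result", followed by the recurring instruction "Data to be presented separately for participants negative for hrHPV", for HPV 16/18 and for other hrHPV.

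The primary disease-burden objective is narrower: "Incidence of CIN2+ in patients with HPV 16/18 by cytology result" and "Incidence of CIN2+ in patients and with other hrHPV with abnormal cytology".

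The Data management section names "laboratory results (cytology, histology, hrHPV, colposcopy records" among its sources, so histology is gathered. Appendix 2 counts as a serious adverse event an "Interval diagnosis of invasive cancer, CIN3, or AIS following a negative hrHPV test".

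**The concern.** An outcome restricted to biopsied participants should give what the pathologist found. As worded, it repeats what the colposcopist saw, in a subset of the same people. Anyone building tables from the list would produce colposcopic impression twice and histology nowhere.

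The CIN2+ item raises a second question. Neighbouring items fix their denominator (those referred, those who had colposcopy, those biopsied). This one says only participants by cytology, and it takes in groups that the care pathway mostly does not send to colposcopy. If those groups stayed in a denominator without verification, their rate would be too low. CIN2+ by HPV type and cytology is a primary objective, and Appendix 3 wants the figure for other hrHPV with low-grade cytology because overseas sources disagree.

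**Working it through.** **1. Wording of the two result items.** They differ only in the population (all with colposcopy; those with a biopsy). The result type and all eight categories are identical. No other listed outcome reports a histological grade, apart from whatever CIN2+ is taken to mean.

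**2. AIS.** The cytology result lists have a combined AGC/AIS row, Appendix 4 counts AIS as high-grade, and Appendix 2 makes it reportable after a negative test. Neither colposcopy result list has an AIS row, so a case can only go under other. CIN2+ is not defined, so whether AIS counts is open.

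**3. Objective against outcome.**

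| Group | In the objective? | In the CIN2+ outcome? | Routine path in the protocol |
|---|---|---|---|
| HPV 16/18, by cytology | yes | yes | colposcopy |
| Other hrHPV, abnormal cytology | yes | yes | colposcopy |
| Other hrHPV, normal cytology | no | yes | repeat screen at 12 months |
| hrHPV negative | no | yes | routine recall; colposcopy mainly through test-of-cure cytology |

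**4. Size of the normal-cytology cell.** The protocol gives no sample size or precision for CIN2+, so there is no figure of that kind to reproduce. Inputs are 3000 screened (Methods). Appendix 4 gives 7% positive (range 5–10%), 25% of positives HPV 16/18, and other hrHPV 45% normal and 35% low-grade. Appendix 3 gives the CIN2+ risks.

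- Check on Appendix 4, per 1000: 70 × 0.25 = 17.5 (stated 18), and 70 × 0.75 × 0.35 = 18.4 (stated about 18). High-grade by subtraction is 20%, giving 70 × 0.75 × 0.20 = 10.5, but Appendix 4 states 8, which implies 8 / 52.5 = 15%. Both are carried below.
- Other hrHPV: 3000 × 0.07 × 0.75 = 157.5.
- Normal cytology: 157.5 × 0.45 = 70.9 (51 at 5% positivity, 101 at 10%). At 9.4% risk: 70.9 × 0.094 = 6.7 CIN2+ (4.8 to 9.5). The 12% that Statistical Considerations assumes for self-tests, applied to all 3000, would give 122 participants and 11.4 cases.
- Low-grade: 157.5 × 0.35 = 55.1. Pooled ASC-US and LSIL risk is (138 + 84) / (498 + 225) = 30.7%, giving 16.9 cases.
- High-grade at 20%: 31.5 × 198/294 = 21.2 cases. At 8 per 1000: 24 × 198/294 = 16.2 cases.

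If every abnormal-cytology participant is verified and no normal-cytology participant is:

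| High-grade share | CIN2+ seen / all other hrHPV | CIN2+ present / all other hrHPV | Share unseen |
|---|---|---|---|
| 20% | 38.1 / 157.5 = 24% | 44.8 / 157.5 = 28% | 15% |
| 15% | 33.1 / 157.5 = 21% | 39.8 / 157.5 = 25% | 17% |

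The percentages do not depend on the positivity rate. Within the normal-cytology cell itself, a per-participant rate reads f × 9.4% if a fraction f is verified at random: 0% at f = 0 and 2.4% at f = 25% (both values of f assumed).

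**5. Cells inside the objective.** Here the only gap is non-attendance or no biopsy. The documents give no attendance figure. Assuming 60%, 80% or 100% verified, unrelated to disease, a true 30.7% in other hrHPV with low-grade cytology (about 55 participants; 39 to 79 at 5–10% positivity) reads 18%, 25% or 31% per participant. It stays at 31% per verified participant.

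**The case against.** The strongest reply is that this is a slip of wording. The visual result is already reported for everyone with colposcopy, so a second item limited to those biopsied makes sense only as the biopsy result. Histology is a named source, pathology records are to be obtained, biopsy is asked for where feasible, and Appendix 4 ties treatment to histological confirmation. A reader might infer that the disease-burden objective rests on colposcopic impression. The documents do not support that: CIN2+ is a separate outcome and nothing defines it by the visual items.

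Other strong readings fail as well.

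- Nowhere does the protocol say that unverified participants count as disease-free. For other hrHPV with low-grade cytology, Appendix 3 points to those referred.
- The hrHPV-negative row is not an error in itself. Test-of-cure patients with abnormal cytology are referred, most hrHPV negatives have no cytology and so would not enter a table by cytology, and a separate row does not distort the other groups.
- It is not established that AIS is excluded from CIN2+; the text leaves this open.

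Denominator detail may also sit in a statistical analysis plan that is not shown, and referrals, biopsies and non-attendance are already to be reported. What remains is that the biopsy item is wrong as written, AIS has no row, and the CIN2+ item reaches cells that its objective leaves out.

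**Conclusion.** The point holds as a minor-to-moderate error of wording and definition. The biopsy outcome duplicates the visual-impression outcome, so no listed outcome reports biopsy histology. AIS has no row. The CIN2+ outcome states neither reference standard nor denominator and covers two groups outside the objective that are mostly not sent to colposcopy.

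The effect is largest outside the objective: about 7 unseen CIN2+ cases (5 to 10 at 5–10% positivity) in other hrHPV with normal cytology, and 24% in place of 28% if all other-hrHPV participants form the denominator. This rests on the overseas risks and cytology shares in Appendices 3 and 4, which the protocol itself calls uncertain for New Zealand, and on no verification in the normal-cytology cell. Inside the objective's groups the effect depends wholly on attendance, which is assumed here. No design change is needed.

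**What to change.** - Reword the biopsy item to report the *histological result (worst grade)*, and add an AIS row to both result lists.
- Define CIN2+ as histologically confirmed CIN2, CIN3, AIS or invasive cancer.
- Report CIN2+ among those verified at colposcopy, with numbers referred and attended beside it in each HPV-by-cytology cell.
- For other hrHPV with normal cytology and for hrHPV negatives, give counts of verified cases only and no incidence.

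The cost is a few lines in the outcome table and, if the case report form mirrors the present lists, one added category. Histology and pathology records are already planned, and most of the referral and attendance counts are already listed. The price in interpretation is that the rates describe those who attended, which the text should state.

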A recommendation for management will be included on the report according to the agreed management protocol after consideration of the patient's screening history and recorded presence or absence of symptoms.

Informing patients

Central recall (mail out)

If the test kit has been supplied directly from the central recall team, participants will be informed of their result by the central study nurse by a combination of letter, phone call, or text (preference will have been requested at the time of taking).

Practice taken or practice coordinated.

The patient will be informed of their result by the practice coordinating nurse or the patient's cervical screener by phone or text or letter as per normal practice.

Unsatisfactory

The test needs to be repeated at the patient's earliest convenience.

Negative hrHPV

A very low risk of cervical abnormality. Repeat screening test at normal recommended interval (*currently 3 years however will increase to 5 years with the new program*). However, if the patient has symptoms they should consult with their doctor. An exception to this is patients due to leave the NCSP screening programme. Please see Appendix 6.

Positive hrHPV (no reflex cytology)

The test has detected the presence of hrHPV. This indicates an increased likelihood of a cervical abnormality. Cervical cancer is very unlikely but further investigation is strongly recommended

HPV16/18

Participants positive for HPV 16 18 will be referred directly to colposcopy without delay. A cervical cytology test at this point is recommended but is not required.

HPV other

The patient will be advised to please make an appointment to undergo an examination and a cervical cytology test (smear) within 2 weeks by a cervical screener of their choice.

The making of appointments will be facilitated by the informant. The patient will be informed that there may be a charge for that appointment.

At this point a patient with a positive result may be referred to colposcopy if cytology triage is considered to be an unacceptable barrier, but the patient agrees to attend colposcopy.

Positive hrHPV with reflex cytology

If a cervical hrHPV sample has been taken and cytology triage has been performed, then this information and or the need to undergo colposcopy can be communicated with the patient face to face or by phone.

Referral to colposcopy

(See flow chart in Appendix 7)

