Clinical override will upgrade the urgency of referral including patients with an abnormal appearing cervix, symptoms, are under-screened or who have perceived barriers will be referred to colposcopy urgently at the discretion of the cervical screener.

Colposcopy and pathology records will be sourced via the provider (with permission of the patient).

Patients with positive hrHPV may be referred to colposcopy in the absence of cytology triage as follows: Pacific and Māori patients, under-screened patients, and patients with HPV16/18.

As identified by the Māori Steering Committee, cervical cytology testing is a probable barrier for Māori patients

(https://www.heiahurumowai.org.nz/_files/ugd/b7edfc_621f3417d3b84349be2ed6372d479d30.pdf). It is particularly important to fully discuss the indications for cervical cytology with patients and to explain that they are able to opt for direct referral to colposcopy without cytology screening, if they would prefer it.

Previous cervical abnormality may also be an indication for referral in the presence of an abnormal hrHPV test.

Colposcopy

Colposcopy will be performed as per standard practice guidelines. Patients who have had no cytology in the last 3 months or normal cytology should have a cytology performed. If feasible at least 1 biopsy should be taken of any visible lesion or the cervical transformation zone. Treatment protocols will adhere to NCSP guidelines. Relevant colposcopy and treatment data will be retrieved to be included in the study dataset.

Patients who do not attend for recommended cytology or colposcopy

The management of these patients should be consistent with normal practice.

Non-attendance for colposcopy is associated with a risk of cancer and every effort should be made to ensure attendance. Where possible a medical practitioner should discuss this with the patient and make an individualised plan for their follow up. The NCSP will be notified.

Patients with hrHPV other following a self-test who decline cytology may be referred to colposcopy. If this is declined where possible a medical practitioner should discuss this with the patient and make an individualised plan for their follow up. The NCSP will be notified. Support to Screen services will be utilised as per normal practice.

Data management

A detailed Data Management Plan is available as a separate document.

All patient data are confidential, and for Māori patients, data are recognised as taonga.

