The Ministry of Health reported NZ average is one full-time equivalent general practitioner (GP) per 1,650 patients and the average practice size is 3 full-time equivalent GPs. Thus, the average GP practice has 4950 patients on their books. Approximately, 32% of the NZ total population is female and between 25 and 65 years old.¹¹ Adding patients between 65 and 69 years and excluding patients who have had a hysterectomy, the average GP practice will have approximately 1600 patients who are eligible for 3-yearly cervical screening and thus, approximately 533 patients due for screening in any one year, and 266 patients due for screening per practice over the 6 month recruitment period. Assuming, 25% of patients do not wish to participate in the study, it would be possible to recruit 200

patients per practice over 6 months. We aim to include 15 general practices as recruitment sites. Thus, that would allow us to recruit 3000 patients over 6 months.

The acceptability and uptake of self-testing varies markedly in different studies depending on country, method of invitation, and demographics of the patients involved.^{8,12} Irrespective, the majority of hrHPV self-sample studies and surveys involve un- or under-screened patients,^{8,12-14} and the uptake in patients who usually participate in screening may differ. However, based on these previous studies, we estimate that 60-70% of patients may opt for self-sampling, thus we estimate that we will recruit 1800-2100 patients to the hrHPV self-sampling group and 900-1200 patients to the clinician-taken hrHPV test group. Based on previous studies,⁴ we estimate that 12% of hrHPV self-sampled tests will be hrHPV positive and an estimated 216-252 patients will need to return to their GP practice so that a follow-up cervical cytology sample can be taken. As this is a key safety concern, the number of patients in the hrHPV self-sample group who do not return for a clinician-taken cervical cytology sample within 3 months following a hrHPV positive result will be assessed. With a sample size of 216, there is 95% power to observe a failure to return rate of 2% or more.

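### The key safety count treats all 216–252 hrHPV-positive self-testers as having to return for cytology, in conflict with the protocol's direct-colposcopy routes and with Appendix 2

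*Protocol*

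**What the plan says.** Statistical Considerations builds the measure in three steps.

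- Group size: "we estimate that we will recruit 1800-2100 patients to the hrHPV self-sampling group".
- Positivity: "we estimate that 12% of hrHPV self-sampled tests will be hrHPV positive".
- Consequence: "an estimated 216-252 patients will need to return to their GP practice so that a follow-up cervical cytology sample can be taken".

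The safety count then covers "patients in the hrHPV self-sample group who do not return for a clinician-taken cervical cytology sample within 3 months following a hrHPV positive result". The sample-size sentence rests on the lower end of the range: "With a sample size of 216, there is 95% power to observe a failure to return rate of 2% or more".

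Other sections describe a different pathway.

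- **Test Results, Informing patients (HPV16/18):** these patients go straight to colposcopy, and "A cervical cytology test at this point is recommended but is not required". The section on cytology triage and the notes to Appendix 6 agree.
- **Referral to colposcopy:** hrHPV-positive patients "may be referred to colposcopy in the absence of cytology triage as follows: Pacific and Māori patients, under-screened patients, and patients with HPV16/18".
- **Non-attendance paragraph in the same part of the protocol:** self-testers with other hrHPV who decline cytology can also be sent to colposcopy.
- **Appendix 2, Serious adverse event reporting:** the cytology event reported at study completion is "A person with other hrHPV who is recommended to have cervical cytology but who does not attend within 3 months". Failure to attend colposcopy within 3 months is a separate event. The Identified risks list makes the same split: missed cytology is a risk for other hrHPV, and missed colposcopy is a major risk for HPV 16/18.

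**The concern.** The protocol singles out one quantity as a key safety concern and sizes it. Both the people at risk and the event are stated in a way that other sections contradict. A patient with HPV 16/18 who goes to colposcopy without a prior smear has followed the protocol. The same holds for a Māori, Pacific or under-screened patient referred without triage. If a return means a visit to the GP practice for cytology, as the sentence giving 216–252 suggests, such a patient is recorded as a failure to return.

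The stated goal is to find where, and for whom, the screening pathway breaks down. A count that can mix permitted pathway use with real loss to follow-up does not answer that. Two definitions of one event also allow two different published figures.

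**Working it through.** **Inputs.** 3000 patients, 60–70% choosing self-testing and 12% positivity (Statistical Considerations). About 25% of positives being HPV 16/18 (Appendix 4). The 2% failure rate in the sample-size sentence.

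**1. The plan's own denominator.** 0.60 × 3000 = 1800 and 0.70 × 3000 = 2100. Then 0.12 × 1800 = 216 and 0.12 × 2100 = 252. The range is reproduced exactly. It equals all positives, so nobody has been removed for genotype or for direct referral.

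**2. Who needs cytology before colposcopy, section by section.**

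| Group | Statistical Considerations | Rest of protocol |
|---|---|---|
| HPV 16/18 | must return for cytology | colposcopy directly; cytology advised, optional |
| Other hrHPV; Māori, Pacific or under-screened | must return | may be referred without cytology |
| Other hrHPV, declines cytology | must return | may be referred to colposcopy |
| Other hrHPV, remainder | must return | cytology is the triage step |

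Only the last row agrees throughout.

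**3. Size of the mismatch for HPV 16/18 alone.** 0.25 × 216 = 54 and 0.25 × 252 = 63. The remainder is 216 − 54 = 162 and 252 − 63 = 189. Direct referrals among other-hrHPV patients would reduce the number relying on cytology further, but the protocol gives no figure for them.

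**4. The precision sentence.** The chance of seeing at least one failure at a true rate of 2% is 1 − 0.98^n.

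- n = 216: 98.7%
- n = 189: 97.8%
- n = 162: 96.2%

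The stated 95% at n = 216 is not this quantity. The chance of at least two failures there is 93.1%. The protocol names no test or null rate that would settle which is meant. On the at-least-one reading, the smaller denominator still gives more than 95%.

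**5. What the count could show (illustration only).** Let s be the share of HPV 16/18 positives with no cytology that counts. The protocol gives no value for s, so these are assumptions. Suppose nobody is truly lost and all other-hrHPV patients have cytology. The apparent failure rate is then 0.25 × s.

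- s = 0: 0%
- s = 0.25: 6.25% (13.5 of 216)
- s = 0.50: 12.5% (27 of 216)
- s = 1: 25% (54 of 216)

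Now suppose a true failure rate of 10% among other-hrHPV patients (assumed). The pooled figure is 0.75 × 0.10 + 0.25 × s, which gives 7.5%, 13.75%, 20% and 32.5% for the same four values. At s = 0 the pooled figure lies below the 10% in the group that relies on cytology.

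**The case against.** A reader might infer that every patient who attends colposcopy promptly without a prior smear is scored as a failure, so that the rate is overstated by a known amount. The protocol does not support that.

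- **Cytology at colposcopy.** The Colposcopy section says cytology should be taken there when none has been done in the previous 3 months. Appendix 6 gives 20 working days for HPV 16/18 referrals, well inside the 3-month window. The count itself asks only for a clinician-taken sample. Only the preceding sentence mentions the GP practice. If a colposcopy sample counts, most of the inflation among attenders disappears. The text does not say whether it does, and that gap is part of the problem.
- **Cytology is still advised for HPV 16/18.** Appendix 3 proposes it for all positives, with exceptions. Describing its uptake in everyone is legitimate. What fails is the claim that all of them need to return.
- **Other reporting covers much of this.** The outcome tables give reasons for missing cytology and times to referral by genotype group, and Appendix 2 reports missed colposcopy separately. That limits the harm. However, direct referral is not among the listed reasons, and Statistical Considerations does not use those reasons to define failure.
- **Equity.** A bias against Māori and Pacific patients is a possibility, not a finding. This count is absent from the outcome tables, and breakdowns are promised only where numbers permit.
- **Stakes.** The study is descriptive. No test, threshold or stopping rule depends on the count, and an analysis plan that is not shown may define it more closely. The protocol's own sections would still disagree.

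**Conclusion.** The point stands as a conflict over the denominator and the event definition. Statistical Considerations puts all 216–252 positives at risk of failing to return for cytology. The pathway sections and Appendix 2 do not. At the protocol's 25% share, 54–63 of them are HPV 16/18 positives who do not need cytology before colposcopy, leaving about 162–189.

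That figure combines the 25% from Appendix 4 with the 12% positivity of Statistical Considerations. Appendix 4 itself works with about 7% positivity, so the absolute numbers are approximate. The one-quarter proportion depends only on the 25%.

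On the GP-practice reading, patients on a permitted route can be counted as failures. No size can be put on the resulting overstatement of loss to follow-up. It could be nil if colposcopy samples count and are taken in time. It could be substantial if they do not count and many patients skip the earlier smear.

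**What to change.** Reconcile Statistical Considerations with Appendix 2 and use one definition in both.

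1. **Group at risk:** self-testers positive for other hrHPV.
2. **Failure:** neither cervical cytology nor colposcopy attended within 3 months of the hrHPV result. State that cytology taken at colposcopy counts as attendance.
3. **HPV 16/18 positives:** report separately the number who did not attend colposcopy within 3 months, and give their cytology uptake descriptively, since cytology is still advised for them.
4. **Numbers:** restate 216–252 as about 162–189, and replace the power sentence with one based on the smaller number. For example, with 162 patients and a true failure rate of 2%, the chance of seeing at least one failure is 96.2%.

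The cost is a wording change and a denominator smaller by about a quarter. The cytology, referral and colposcopy timings are already listed as outcomes. Only the analysis definition changes; no clinical referral rule is altered.
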